14.2.1 Secondary Objective: Analysis of Disease-Free Survival

Table 7 Summary of analysis of the Disease-Free Survival

Analysis Population	Derivation	Statistical Analysis Methods	Missing data handling
Secondary endpoint: Disease-Free Survival			
FAS	Disease-free Survival time, defined as the time from first treatment day to the date of the first documentation of objective PD or death due to any cause, whichever occurs first.	Kaplan-Meier estimates will be presented overall, together with a summary of associated statistics (median survival time and survival rate estimates) including the corresponding 2-sided 95% CIs. Confidence intervals for the median will be calculated according to Brookmeyer and Crowley (Brookmeyer & Crowley, 1982) and CIs for the survival function estimates will be derived using the log-log transformation according to Kalbfleisch and Prentice (Kalbfleisch & RL, 1980): conftype=loglog default option in SAS Proc LIFETEST. The estimate of the standard error will be computed using Greenwood's formula	Model based

CI = Confidence interval; FAS = Full analysis set; PD = Progressive disease

14.3 Secondary Endpoint: Local Recurrence and/or Distant Metastasis

Population: FAS analysis set (participants with surgery only)

Time from surgery to local recurrence will be defined as time from day of surgery to the date of the first documentation of progression of disease, flagged as 'local recurrence' or 'local recurrence and distant metastasis' ('TUMOR ASSESSMENT(ACCORDING TO NCCN) DURING LONG-TERM SAFETY AND SURVIVAL FOLLOW-UP' eCRF page).

Time from surgery to distant metastasis will be defined as time from day of surgery to the date of the first documentation of progression of disease, flagged as 'distant metastasis' or 'local recurrence and distant metastasis' ('TUMOR ASSESSMENT(ACCORDING TO NCCN) DURING LONG-TERM SAFETY AND SURVIVAL FOLLOW-UP' eCRF page). Only subjects who undergo rectal surgery (week 15) will be included in this analysis.

Table 8 Date of event / censoring definition for Local/Distant recurrence Analysis

	Status	Censoring	Date of event / censoring
Time to local recurrence: PD flagged as 'Local recurrence' or 'Local recurrence and distant metastasis'	No consecutive missing tumor assessments	Event	Date of progression
	After two or more subsequent missing tumor assessments (i.e. 2 times the scheduled time interval between two subsequent response assessments)	Censored	Date of last tumor assessment with outcome CR or date of surgery, whatever is later
Time to distant metastasis: PD flagged as 'Distant metastasis' or 'Local recurrence and distant metastasis'	Time to local recurrence: No consecutive missing tumor assessments and PD flagged as 'Distant metastasis'	Censored	Date of progression
	Time to distant metastasis: No consecutive missing tumor assessments and PD flagged as 'Local recurrence'		
No PD flagged as 'Local recurrence', 'Distant metastasis' or 'Local Recurrence and Distant metastasis' and no missed tumor assessment		Censored	Date of last tumor assessment with outcome CR or date of surgery, whatever is later

CR = Complete response; PD = Progressive disease

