8.1.2.2 Tumor Response Evaluation

After induction chemotherapy: Response evaluation after induction chemotherapy and restaging before study intervention with peposertib and CRT are provided in [Appendix 5](#). The evaluation with MRI, endoscopy, and DRE is to be done before starting treatment/randomization (peposertib and CRT). Overall response is evaluated as progressive disease, stable disease, partial response, nearly complete response, or complete response. Participants who present with stable disease, partial response, or nearly complete response may enter the study, participants who present with tumor progression or cCR should be treated according to standard practice per institutional guidelines.

After peposertib and CRT: Response evaluation criteria after treatment and restaging before surgery are provided in [Appendix 5](#). The evaluation with MRI, endoscopy, and DRE is to be done at Week 14 (± 7 days). Overall response is evaluated as progressive disease, incomplete response, nearly complete response, or complete response.

During Long-term Safety Follow-up: Response evaluation is provided in [Appendix 5](#).

If a scan shows progressive disease, it will be indicated whether it is local recurrence, distant recurrence, or both.

Tumor assessments are performed until progressive disease or the participant withdrawal of consent. Tumor assessments will be stopped on subsequent start of new anticancer therapy, with the exception of starting adjuvant treatment described in [Section 6.5](#).

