9.4.1 Efficacy Analyses

Statistical analysis methods for efficacy endpoints are described in [Table 12](#).

Table 12 Statistical Analysis Methods for Efficacy Endpoints

Endpoint	Statistical Analysis Methods
Secondary	
Composite endpoint of pCR/cCR	Derivation of the pCR/cCR composite endpoint (pCR based on local review) is described in Section 3.1 . The proportion of participants with pCR/cCR is indicated together with the 95%-Clopper-Pearson CI. The analysis will be performed on the FAS.
Disease-Free Survival	Disease-free Survival time, defined as the time from first treatment day to the date of the first documentation of objective progressive disease or death due to any cause, whichever occurs first. The analysis will be performed as described below for time-to-event endpoints.
pCR	The definition of pCR is provided in Section 3.1 . pCR will be analyzed once on the local review of the histology slides. The proportion of participants with pCR will be reported together with the corresponding 95% CIs. The analysis will be performed on the FAS

Endpoint	Statistical Analysis Methods
cCR	The definition of cCR is provided in Section 3.1. The proportion of participants with cCR will be reported together with the corresponding 95% CIs. The analysis will be performed on the FAS
Local/distant recurrence	The following analyses will be performed: 
 • Time from surgery to local recurrence • Time from surgery to distant recurrence. The analyses will be performed as described below for time-to-event endpoints.
Neoadjuvant Rectal Score	The neoadjuvant rectal score will be presented in terms of summary statistics (such as mean, median, standard deviation, and quartiles) and graphically. The analysis will be performed on the FAS Population.

cCR=Clinical Complete Response, CI=confidence interval, CR=complete response, FAS=Full Analysis Set, pCR=Pathological Complete Response.

In addition to analyses specified in [Table 12](#), for the primary and main secondary endpoints subgroup analyses on baseline variables such as gender, tumor stage, etc. will be performed.

Analysis of Time-to-event Endpoints

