Kaplan-Meier estimates will be presented together with a summary of associated statistics (median survival time and survival rate estimates) including the corresponding 2-sided 95% CIs. Confidence intervals for the median will be calculated according to Brookmeyer and Crowley ([Brookmeyer 1982](#)) and CIs for the survival function estimates will be derived using the log-log transformation according to Kalbfleisch and Prentice ([Kalbfleisch 1980](#)). The estimate of the standard error will be computed using Greenwood’s formula.

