14.3.1 Secondary Objective: Analysis of Local Recurrence and/or Distant Metastasis

Table 9 Summary of the analysis of the local recurrence and/or distant metastasis

Analysis Population	Derivation	Statistical Analysis Methods	Missing data handling
FAS	The following analyses will be performed: 
 • Time from surgery to local recurrence • Time from surgery to distant metastasis. 	Kaplan-Meier estimates will be presented overall, together with a summary of associated statistics (median survival time and survival rate estimates) including the corresponding 2-sided 95% CIs. Confidence intervals for the median will be calculated according to Brookmeyer and Crowley (Brookmeyer & Crowley, 1982) and CIs for the survival function estimates will be derived using the log-log transformation according to Kalbfleisch and Prentice (Kalbfleisch & RL, 1980): conftype=loglog default option in SAS Proc LIFETEST. The estimate of the standard error will be computed using Greenwood's formula	Model based

CI = Confidence interval; FAS = Full analysis set

The listing of tumor assessments prior Surgery (including Screening tumor assessments) and all relevant informations as recorded on the 'TUMOR ASSESSMENT (ACCORDING TO NCCN) AFTER RADIOTHERAPY in ETT/WEEK14' and 'TUMOR ASSESSMENT (ACCORDING TO NCCN) DURING LONG-TERM SAFETY and SURVIVAL FOLLOW-UP' eCRF pages, will be provided by subject.

A swimmer plot displaying some key radiological milestones as well as surgery will be produced, sorted by follow-up time. For the purpose of CSR, a version of the swimmer plot without subject id will be provided. For each subject, the time from treatment start until end of follow-up will be represented (from treatment start to last date known to be alive or date of death). In addition, the following information will be displayed: time of first occurrence of CR, Nearly-CR, IR, and PD, time of surgery, pCR achievement and status at the end of the follow-up (alive or dead).

In addition, a listing will be provided summarizing all of the efficacy endpoints (as defined above) for each participant. This listing will include dose level, subject identification number, date of first dose, date of last evaluable tumor assessment, efficacy endpoint, and event. In addition, for DFS, and local/distant recurrence, event/censor date, censor flag, and the time-to-event/censoring will be included.

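### Local recurrence and distant metastasis are competing first failures, but only Kaplan-Meier is planned; 1 − KM read as recurrence risk is at or above the cumulative incidence, and Table 8 leaves some participants without a censoring rule

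*SAP*

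**What the plan says.** **Event and censoring rules.** SAP 14.3 times each endpoint from the Week 15 surgery to first progression of the relevant type. Progression flagged as both types is an event in both analyses. Progression of the other type alone is censored at the progression date; for local recurrence the row reads "Time to local recurrence: No consecutive missing tumor assessments and PD flagged as" distant metastasis. A recurrence found "After two or more subsequent missing tumor assessments" is censored at the last complete-response assessment or at surgery, whichever is later. The last row, for participants with no flagged progression, carries the condition "and no missed tumor assessment".

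**Follow-up.** Protocol 8.1.2.2 says: "If a scan shows progressive disease, it will be indicated whether it is local recurrence, distant recurrence, or both". It also says: "Tumor assessments are performed until progressive disease or the participant withdrawal of consent".

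**Estimator.** SAP Table 9 says: "Kaplan-Meier estimates will be presented overall, together with a summary of associated statistics (median survival time and survival rate estimates", and names no time at which the rates are read. Protocol Table 12 (section 9.4.1) says of local and distant recurrence: "The analyses will be performed as described below for time-to-event endpoints". The method it points to is the same: "Kaplan-Meier estimates will be presented together with a summary of associated statistics (median survival time and survival rate estimates".

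Neither document mentions competing risks or cumulative incidence for these endpoints.

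**The concern.** Once a participant has distant-only progression, scanning ends and a later local recurrence will not be seen; the same holds the other way round. Kaplan-Meier with the other type censored describes a setting in which that other type does not occur. A reader of the study report, or of a manuscript drawn from it, may take 1 minus the reported rate as the share of operated participants whose disease returned locally (or distantly). It is not that share once a competing failure has come before an event of interest.

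The second problem does not depend on the first. A participant with no progression who missed an assessment, alive or dead, fits no row of Table 8, so the programmer has to invent a rule. Only three scans follow surgery (Weeks 27, 39 and 52), so a missed one is plausible.

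**Working it through.** The documents give no rate, event count or number operated on for these endpoints, so there is no figure of the plan to reproduce. The check has four parts.

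**1. Direction.** At each event time u, let n be the number at risk and d the events of the type analysed. Let S_c be Kaplan-Meier survival with the other type censored, and S_all the survival free of either type. Then:

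- 1 − KM(t) = Σ S_c(u−) · d/n
- Aalen-Johansen AJ(t) = Σ S_all(u−) · d/n

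The risk sets are the same and S_c ≥ S_all, so 1 − KM ≥ AJ in every data set. They are equal when no competing failure precedes an event of interest. In 40,000 comparisons on simulated data (n from 5 to 19, with ties and random censoring), 1 − KM was below AJ in none, equal in 20,077 and above in 19,923.

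**2. The mechanism by hand (assumed data, common visit times).** Take 16 operated on, with 2 distant-only failures at Week 27, then 1 local and 1 distant-only failure at each of Weeks 39 and 52. The numbers at risk are 16, 14 and 12. For local recurrence:

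- 1 − KM = 1 − (13/14)(11/12) = 25/168 = 14.9%
- AJ = (14/16)(1/14) + (12/16)(1/12) = 2/16 = 12.5%

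This shows how the gap arises. It does not show its likely size, because real scans spread over the visit windows.

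**3. Size, with the windows.** Surgery is at Week 15 ± 2 weeks (protocol 4.1.3) and the Week 52 visit has a window of ± 2 weeks (protocol Table 2). After surgery, the Week 52 scan therefore falls at:

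- nominally 52 − 15 = 37 weeks
- earliest (52 − 2) − (15 + 2) = 33 weeks
- latest (52 + 2) − (15 − 2) = 41 weeks

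The latest in-window Week 39 scan is at (39 + 2) − (15 − 2) = 28 weeks. Assume n = 16, 2 local and 4 distant-only failures spread equally over the three visits, uniform timing within the windows, and no other loss. Simulation gives, for local recurrence (crude 2/16 = 12.5%):

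| Weeks after surgery | Mean AJ | Mean excess of 1 − KM |
|---|---|---|
| 33 | 8.3% | about 0.8 points |
| 37 | 11.1% | about 1.6 points |
| 41 | about 19% | about 5 points |

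The 33-week value is as expected: two thirds of failures occur at Weeks 27 and 39, and 12.5% × 2/3 = 8.3%. At 41 weeks the risk set is empty in essentially all runs and the 97.5th percentile of AJ is about 70%. That row is an artefact of the thin tail.

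**4. The missed-assessment rule can pull the other way.** Suppose 1 of 2 local recurrences in 16 is first seen at Week 52 after missed scans at Weeks 27 and 39, with no other failures. Table 8 censors it at surgery, and the estimate falls from 2/16 = 12.5% to 1/15 = 6.7%, a drop of 5.8 points. For scale, the exact 95% interval for 2/16 is 1.6% to 38.3%.

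**The case against.** The strongest reply is that nothing here is wrong as written. Censoring the other failure type is the ordinary cause-specific analysis, and the SAP reports survival rates; it never says that 1 − KM will be presented as risk. No hypothesis is tested. The participant listing in SAP 14.3.1 shows each event or censoring date and flag. All of this stands, and it limits the point to labelling and completeness.

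Four stronger readings are tempting and should be resisted:

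- *That the planned Kaplan-Meier analysis is invalid.* It is valid as a net summary. Only the reading as a probability of recurrence fails.
- *That the gap is large, or that it is exactly zero in a known share of trials.* The documents give no event counts. Figures that put all scans at three common times ignore the stated windows and should not be relied on.
- *That 41 weeks is the natural landmark because it takes in every in-window Week 52 scan.* Under the visit schedule hardly anyone is still at risk then, so the estimate there is less stable than the problem it would solve.
- *That the DFS analysis has the same hole, because SAP Table 6 repeats the condition for event-free survivors.* It does not: the text of SAP 14.2 censors all event-free participants at their last adequate assessment. SAP 14.3 has no such sentence.

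**Conclusion.** The point holds in limited form. The direction is algebraic and rests on no assumed counts: under Table 8, 1 − KM is at or above the cumulative incidence of that first failure type. The size cannot be derived from the documents. Under the assumptions above it averages about 1 point at 33 weeks and 1.6 points at 37 weeks, small beside the sampling uncertainty. The assumed 16 is a scenario: the protocol reports 19 treated as of 06 May 2021 but not how many had surgery. The model has three scans per participant; scans beyond one year, which some participants may have had before amendment 4.0, are not in it and would thicken the late risk set.

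The Table 8 gap is a plain omission, whatever the size of the excess. The dose-limiting toxicity endpoint is unaffected, and no decision rule uses these endpoints. This is a cheap improvement, not a threat to the trial's conclusions.

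**What to change.** - **SAP 14.3.1:** add Aalen-Johansen cumulative incidence of local recurrence and of distant metastasis, timed from surgery, with 95% confidence intervals and numbers at risk. Treat the other first failure type and death without recurrence as competing events. Count simultaneous local and distant progression in both, as now, and note that the two incidences therefore overlap and cannot be added.
- **Label** the retained Kaplan-Meier output cause-specific (net).
- **Time point:** read the estimates when event-free participants are still at risk, such as 33 weeks after surgery (the earliest in-window Week 52 scan), and not at 41 weeks. Later Week 52 events fall after that cut, so also give crude first-failure counts by type through Week 52.
- **Table 8, last row:** reword it to cover every participant with no progression, alive or dead, with or without missed assessments. Apply the rule on two or more missed assessments identically to both failure types and to death, with a sensitivity analysis that counts those events.
- **SAP section 7:** record the change from protocol 9.4.1.

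The cost is one added estimator, one sensitivity analysis, a table rewording and a section 7 entry. No new data or visits are needed.

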14.3.1 Secondary Objective: Analysis of Local Recurrence and/or Distant Metastasis

Table 9 Summary of the analysis of the local recurrence and/or distant metastasis

Analysis Population	Derivation	Statistical Analysis Methods	Missing data handling
FAS	The following analyses will be performed: 
 • Time from surgery to local recurrence • Time from surgery to distant metastasis. 	Kaplan-Meier estimates will be presented overall, together with a summary of associated statistics (median survival time and survival rate estimates) including the corresponding 2-sided 95% CIs. Confidence intervals for the median will be calculated according to Brookmeyer and Crowley (Brookmeyer & Crowley, 1982) and CIs for the survival function estimates will be derived using the log-log transformation according to Kalbfleisch and Prentice (Kalbfleisch & RL, 1980): conftype=loglog default option in SAS Proc LIFETEST. The estimate of the standard error will be computed using Greenwood's formula	Model based

CI = Confidence interval; FAS = Full analysis set

The listing of tumor assessments prior Surgery (including Screening tumor assessments) and all relevant informations as recorded on the 'TUMOR ASSESSMENT (ACCORDING TO NCCN) AFTER RADIOTHERAPY in ETT/WEEK14' and 'TUMOR ASSESSMENT (ACCORDING TO NCCN) DURING LONG-TERM SAFETY and SURVIVAL FOLLOW-UP' eCRF pages, will be provided by subject.

A swimmer plot displaying some key radiological milestones as well as surgery will be produced, sorted by follow-up time. For the purpose of CSR, a version of the swimmer plot without subject id will be provided. For each subject, the time from treatment start until end of follow-up will be represented (from treatment start to last date known to be alive or date of death). In addition, the following information will be displayed: time of first occurrence of CR, Nearly-CR, IR, and PD, time of surgery, pCR achievement and status at the end of the follow-up (alive or dead).

In addition, a listing will be provided summarizing all of the efficacy endpoints (as defined above) for each participant. This listing will include dose level, subject identification number, date of first dose, date of last evaluable tumor assessment, efficacy endpoint, and event. In addition, for DFS, and local/distant recurrence, event/censor date, censor flag, and the time-to-event/censoring will be included.

Finally, all tumor assessments performed during the long-term safety and survival follow-up period will be listed. This listing will include dose level, subject identification number, assessment

visit, imaging date, assessment method and the overall status. This listing will be sorted by dose level, subject identification number and Imaging date.

14.4 Secondary Endpoint: Neoadjuvant Rectal Score

Population: FAS analysis set

The neoadjuvant rectal score (NAR) was developed by George and colleagues to serve as a short term clinical study surrogate endpoint (George 2015). The Valentini nomograms (Valentini 2011) to predict overall survival in rectal cancer patients after neoadjuvant treatment are the basis of the NAR score. Its score ranges from 0 to 100, whereas a score close to 100 is indicative of a poorer prognosis.

14.4.1 Secondary Objective: Analysis of NAR score

Table 10 Summary of the analysis of the NAR score

Analysis Population	Derivation	Statistical Analysis Methods	Missing data handling
FAS	See NAR formula below.	The neoadjuvant rectal score will be presented in terms of summary statistics (such as mean, median, standard deviation, and quartiles) and graphically using a boxplot by dose level.	Participants with at least one item of the NAR score missing will be considered as having a missing NAR score.

FAS = Full analysis set

The Neoadjuvant Rectal Score (NAR) will be calculated using a formula that includes the clinical tumor (cT) stage, pathologic tumor (pT), and node (pN) stage according to the tumor, node, metastasis classification system for colorectal cancers. The NAR score is calculated as follows:

$$NAR = \frac{[5pN - 3(cT - pT) + 12]^2}{9.61}$$

Where cT is an element of the set {1, 2, 3, 4}, pT is in {0, 1, 2, 3, 4}, and pN is in {0, 1, 2}.

cT is collected on the “DISEASE HISTORY” eCRF page, from the “TNM classification at study entry” item, as follows:

- Numeric part of the T stage = cT

pN and pT are collected on the “TUMOR EVALUATION – WEEK 15” eCRF page, from the “ypTNM score”, as follows:

- Numeric part of the N stage = pN
- Numeric part of the T stage = pT

The listing of NAR score and all relevant informations for calculation pN and cT from 'DISEASE HISTORY' eCRF page and PT from 'TUMOR EVALUATION – WEEK 15' eCRF page, will be provided by subject.

15 Safety Analyses

The subsections in this section include specifications for summarizing safety endpoints that are common across clinical studies such as AE, laboratory tests and vital signs.

The primary endpoint of the Phase Ib is the occurrence of DLTs during the DLT observation period (5.5 weeks after the start of treatment). Based on the data observed, a recommendation of the next dose level is based on a Bayesian dose escalation design using a two-parametric logistic regression model. More details about the analysis to be provided to SMC members are presented in a dedicated IAP.

